7.1.2.2. Permanent discontinuation

[figure not shown]
Study treatment will be discontinued for a participant if the following haematological stopping criteria are met:

- Absolute neutrophil count $<0.5 \times 10^9/L$ on any occasion (confirmed on repeat testing within 3-5 days).
- Absolute neutrophil count $<1.0 \times 10^9/L$ for 2 weeks.
- Grade 3 febrile neutropaenia (neutrophil count $<1.0 \times 10^9/L$ and fever $\geq 38.5^{\circ}C$).

Treatment restart or re-challenge for these participants is not allowed. The Investigator must immediately inform the Medical Monitor of the event, and repeat testing must be conducted at an appropriate frequency until haematological laboratory values have returned to above the lower limit of normal.

7.1.3. Liver Chemistry Stopping Criteria

Liver chemistry stopping and increased monitoring criteria have been designed (see algorithm below) to assure participant safety and evaluate liver event aetiology.

Abbreviations: ALT = alanine transaminase; INR = international normalized ratio; SAE = serious adverse event; ULN = upper limit of normal.

Symptoms of liver injury or hypersensitivity include: fatigue, nausea, vomiting, right upper quadrant pain or tenderness, fever, rash, and/or eosinophilia.

Liver Safety Required Actions and Follow up Assessments Section can be found in [Appendix 6](#), Section [10.6](#).

7.1.4. QTc Stopping Criteria

A participant who meets the bulleted criteria based on the average of triplicate ECG readings will discontinue study treatment:

- QTc >500 msec OR uncorrected QT >600 msec.
- Change from baseline of QTc >60 msec.

7.1.5. Group and Study Safety Stopping Criteria

In addition to the individual stopping criteria specified above, blinded data of AEs, SAEs, laboratory abnormalities, ECG abnormalities, and changes in vital signs occurring across all randomised participants will be regularly reviewed by the SRT to ensure appropriate participant safety.

Study stopping criteria have been set with respect to numbers of individual permanent discontinuations due to neutropaenia attributable to GSK2831781 (see Section [7.1.2.2](#)):

- ≥ 2 participants, in up to 9 participants dosed in the study.
- ≥ 5 participants, in up to 60 participants dosed in the study.
- $>10\%$ of participants for the remainder of the study.

Rates meeting these thresholds will trigger an ad hoc DRC review, to determine whether neutropaenia is likely to be attributable to GSK2831781. Furthermore, the study may be terminated prematurely if there are new toxicological findings, SAEs or frequent AEs that invalidate the positive benefit-risk assessment. Any changes to the study due to safety reasons will be promptly communicated to the appropriate Regulatory Authorities.

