7. DISCONTINUATION OF STUDY INTERVENTION AND PARTICIPANT DISCONTINUATION/WITHDRAWAL

An SRT will oversee the safety of participants in this study. The SRT will review blinded safety data at regular intervals during the study and ad hoc as required, and have oversight of any emerging safety data related to GSK2831781, as described in the SRT charter. The DRC will review unblinded safety and efficacy data at defined intervals. Full details are included in the DRC Charter.

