10.3.4. Recording and Follow-Up of AE and SAE

AE and SAE Recording

When an AE/SAE occurs, it is the responsibility of the Investigator to review all documentation (e.g. hospital progress notes, laboratory, and diagnostics reports) related to the event.The Investigator will then record all relevant AE/SAE information in the CRF.It is not acceptable for the Investigator to send photocopies of the participant's medical records to GSK in lieu of completion of the GSK AE/SAE CRF page.There may be instances when copies of medical records for certain cases are requested by GSK. In this case, all participant identifiers, with the exception of the participant number, will be redacted on the copies of the medical records before submission to GSK.The Investigator will attempt to establish a diagnosis of the event based on signs, symptoms, and/or other clinical information. Whenever possible, the diagnosis (not the individual signs/symptoms) will be documented as the AE/SAE.
Assessment of Intensity

The Investigator will make an assessment of intensity for each AE and SAE reported during the study and assign it to 1 of the following categories:
 
Mild: An event that is easily tolerated by the participant, causing minimal discomfort and not interfering with everyday activities.Moderate: An event that causes sufficient discomfort and interferes with normal everyday activities.Severe: An event that prevents normal everyday activities. An AE that is assessed as severe should not be confused with an SAE. Severe is a category utilized for rating the intensity of an event; and both AE and SAE can be assessed as severe. 
An event is defined as 'serious' when it meets at least 1 of the predefined outcomes as described in the definition of an SAE, NOT when it is rated as severe.

Assessment of Causality

The Investigator is obligated to assess the relationship between study intervention and each occurrence of each AE/SAE.A "reasonable possibility" of a relationship conveys that there are facts, evidence, and/or arguments to suggest a causal relationship, rather than a relationship cannot be ruled out.

- The Investigator will use clinical judgment to determine the relationship.

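### The neutropaenia review trigger counts only discontinuations already attributed to GSK2831781, although the review it triggers is what settles attribution

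*Protocol*

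**What the plan says.** Protocol 7.1.5 places its study-level limits on "numbers of individual permanent discontinuations due to neutropaenia attributable to GSK2831781" and refers to 7.1.2.2 for the individual criteria. The limits are at least 2 participants "in up to 9 participants dosed in the study", at least 5 "in up to 60 participants dosed in the study", and more than 10% after that. It continues: "Rates meeting these thresholds will trigger an ad hoc DRC review, to determine whether neutropaenia is likely to be attributable to GSK2831781".

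Section 7.1.2.2 defines permanent discontinuation by neutrophil count and fever alone. It asks nothing about cause, and adds that "The Investigator must immediately inform the Medical Monitor of the event".

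Routine oversight is blinded. Protocol 7 states: "The SRT will review blinded safety data at regular intervals during the study and ad hoc as required". Unblinded safety data go to the DRC. Under 6.4.2, site staff are blinded except for pharmacists or their delegates.

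The only case-level attribution step in the protocol is in 10.3.4: "The Investigator is obligated to assess the relationship between study intervention and each occurrence of each AE/SAE". Section 7.1.5 does not refer to it. The SAP does not restate the trigger.

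**The concern.** Attribution appears twice in one short rule: as the condition for counting a case, and as the question put to the committee once enough cases are counted. Followed as written, somebody must sort cases by cause before the only body with routine access to treatment codes has looked. Cases set aside at that point do not count towards the limit, so a true drug effect could take longer to reach the DRC.

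Neutropaenia is the first product risk listed in Protocol 2.3.1, with adverse findings in monkeys, and Protocol 4.2 describes this as the first repeat-dose study. A trigger that works early is therefore worth having. What is at stake is the promptness of an ad hoc unblinded review.

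**Working it through.** **Text.** Three provisions, side by side:

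- 7.1.5 counts attributable cases only and does not say who attributes them.
- 7.1.2.2 supplies cases with no attribution step.
- 10.3.4 gives a blinded investigator's opinion, and asks for positive grounds to suspect the drug; being unable to exclude it is not enough.

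Nothing links 10.3.4 to the count in 7.1.5, so the pre-review filter is required but undefined.

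**Inputs.** From the protocol: the limits 2 of 9 and 5 of 60 (7.1.5), and the early 2:1 allocation to 450 mg or placebo (4.1). Assumed: a rate p of qualifying discontinuations per participant dosed, placebo included, and a share q of those cases called attributable before the review. The protocol states no operating characteristics for this rule, so there is no figure of its own to reproduce. The 10% rate is chosen because it is the protocol's later limit. With no placebo cases, 10% overall is 0.10 / (2/3) = 15% on active.

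**Formulas.** The counted rate is r = p × q.

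- P(at least 2 of 9) = 1 − (1−r)^9 − 9r(1−r)^8
- P(at least 5 of 60) = 1 − Σ(k=0..4) C(60,k) r^k (1−r)^(60−k)

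At r = 0.10 the first is 1 − 0.3874 − 0.3874 = 0.225. The second is 1 − (0.0018 + 0.0120 + 0.0393 + 0.0844 + 0.1336) = 0.729.

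| p | q | r | ≥2 of 9 | ≥5 of 60 |
|---|---|---|---|---|
| 10% | 100% | 10% | 22.5% | 72.9% |
| 10% | 75% | 7.5% | 14.2% | 47.2% |
| 10% | 50% | 5% | 7.1% | 18.0% |
| 5% | 100% | 5% | 7.1% | 18.0% |
| 5% | 75% | 3.75% | 4.2% | 7.4% |
| 5% | 50% | 2.5% | 2.0% | 1.7% |

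The third limit is thinned in the same way. For the counted rate to exceed 10%, the true rate must exceed 10/0.75 = 13.3% at q = 75%, or 10/0.5 = 20% at q = 50%.

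**Cost of dropping the filter.** Suppose every case counts, the limits belong to the first 9 and first 60 dosed, and confirmation lags by an assumed 5 dosings. By 65 dosed, the first 60 are then confirmable. An exact participant-by-participant calculation gives the total chance of any review. It should lie between the larger of the two single-limit probabilities and their sum, and it does.

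| Background rate | ≥2 of 9 | ≥5 of 60 | Any review by 65 dosed |
|---|---|---|---|
| 1% | 0.34% | 0.03% | 0.4% |
| 2% | 1.31% | 0.70% | 1.9% |
| 5% | 7.12% | 18.03% | 21.6% |

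The last column is a ceiling on the added reviews. It is reached only if the filter would have removed every background case.

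**The case against.** The rule can be read as two ordinary stages: case-level suspicion produces a count, and the DRC then decides at group level whether the drug is the likely cause. The reference to 7.1.2.2 could also be read as meaning that all such discontinuations count, which is the change proposed here. Assessment before the review is not wholly blinded either, since 6.4.2 lets the sponsor's pharmacovigilance staff unblind any participant with an SAE. Investigators must consult the Investigator's Brochure when assessing causality, so a 50% share may be pessimistic. Section 2.3.1 reports no neutropaenia in the human single-dose data. The SRT and DRC charters, which may hold counting rules, are not among the documents.

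Much of this stands, and a reader should not infer that the trigger is unworkable. What it does not do is supply a counting rule. The two-stage reading still leaves the first stage to people who are generally blinded, SAE unblinding need not cover every 7.1.2.2 case, and 7.1.5 points to neither 6.4.2 nor 10.3.4.

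A reader might also infer a hole in the bands: that once the 10th participant is dosed, late-confirmed events among the first 9 face a limit of 5 instead of 2. At a 10% rate and a lag of 5 dosings, that would give 5.2% against 22.5% by 14 dosed. The documents do not establish this. The wording naturally pairs a numerator with a denominator, and on that reading no gap exists. The point is missing detail and not a demonstrated error.

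Nor do the documents show that unblinded safety review is absent before Interim Analysis 3. The table row for Interim Analysis 1 lists only PK, but Protocol 9.5 and 10.1.5 describe DRC review of safety at the interims in general.

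**Conclusion.** The point holds as a weakness in how the count is defined. Section 7.1.5 filters on a judgement that the triggered review exists to make, and any such filter lowers sensitivity. At an assumed 10% rate, calling half the cases attributable cuts the chance of reaching 2 of 9 from 22.5% to 7%, and of reaching 5 of 60 from 73% to 18%. The direction follows from the text; the size rests on assumed rates and shares.

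The consequence is modest. The thresholds lead to a review and not a stop. Each case goes at once to the Medical Monitor, the SRT can meet ad hoc, and the individual stopping rules apply. Recruitment may be paused (Protocol 4.1) and need not continue through an interim if there is a safety concern (9.5). SAP 15.12.3 lists a blinded safety summary at 30 participants, and SAP 3.1 has unblinded safety data reviewed at Interim Analysis 3. The sponsor ended the study on 14-JAN-2021 (SAP 2.1), so practical reach is small. This is an optional, low-cost improvement.

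**What to change.** In Protocol 7.1.5, count every permanent discontinuation that meets 7.1.2.2, whatever its suspected cause, and leave attribution to the unblinded DRC. Keep the three thresholds. The Medical Monitor notices under 7.1.2.2 already provide the count.

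As a minor clarification, state that the limits of 2 and 5 apply to events among the first 9 and first 60 participants dosed, whenever those events are confirmed. Bring the SRT and DRC charters into line; if they already say this, a cross-reference in 7.1.5 is enough.

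The cost is a few sentences and some additional ad hoc unblinded reviews, bounded by the background-rate table above: negligible at 1% or 2%, about one chance in five at 5%.

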7.1.6. Temporary withholding of IP

Temporary withholding of IP may occur in the event of:

- Meeting treatment withholding criteria for neutropaenia (see Section [7.1.2.1](#))
- In the event of a clinically significant infection that the Investigator believes may be related to, or exacerbated by, ongoing treatment with the study drug, and none of the permanent stopping rules have been met.
- In the event that the participant has a close household contact with a highly transmissible infection, the Investigator has discretion to delay dosing.

If the scheduled dose window is missed, re-initiation of study treatment intervention should be restarted as soon as possible but should not result in two consecutive doses, whether IV or SC, being given less than 7 days apart (see Section [6.5](#)).

7.2. Participant Discontinuation/Withdrawal from the Study

A participant may withdraw from the study at any time at his/her own request, or may be withdrawn at any time at the discretion of the Investigator for safety, behavioural, compliance or administrative reasons.

At the time of discontinuing study treatment, participants should be encouraged to stay on schedule and attend all remaining visits set out in the SoA (Section 1.3) until the end of the current study phase. An Early withdrawal visit is only required for participants who prematurely discontinue study treatment and do not agree to complete the remaining scheduled visits for that phase. In both cases, all participants should undertake a Follow-Up visit approximately 16 weeks from the last dose received, where the participant will be permanently discontinued from the study at that time.

If the participant withdraws consent for disclosure of future information, the sponsor may retain and continue to use any data collected before such a withdrawal of consent.

If a participant withdraws from the study, he/she may request destruction of any samples taken and not tested, and the Investigator must document this in the site study records.

7.3. Lost to Follow-Up

A participant will be considered lost to follow-up if he or she repeatedly fails to return for scheduled visits and is unable to be contacted by the study site.

The following actions must be taken if a participant fails to return to the clinic for a required study visit:

- The site must attempt to contact the participant and reschedule the missed visit as soon as possible and counsel the participant on the importance of maintaining the assigned visit schedule and ascertain whether or not the participant wishes to and/or should continue in the study.
- Before a participant is deemed lost to follow-up, the Investigator or designee must make every effort to regain contact with the participant (where possible, 3 telephone calls and, if necessary, a certified letter to the participant's last known mailing address or local equivalent methods). These contact attempts should be documented in the participant's medical record.
- Should the participant continue to be unreachable, he/she will be considered to have withdrawn from the study.

Discontinuation of specific sites or of the study as a whole are handled as part of [Appendix 1](#), Section [10.1.9](#).

8. STUDY ASSESSMENTS AND PROCEDURES

- A signed, written informed consent form must be obtained from the participant prior to any study-specific procedures or assessments being performed.
- Study procedures and their timing are summarized in Section 1.3.
- Protocol waivers or exemptions are not allowed.
- Immediate safety concerns should be discussed with the Sponsor immediately upon occurrence or awareness to determine if the participant should continue or discontinue study intervention.
- Adherence to the study design requirements, including those specified in the SoA (Section 1.3), is essential and required for study conduct.
- All screening evaluations must be completed and reviewed to confirm that potential participants meet all eligibility criteria. The Investigator will maintain a screening log to record details of all participants screened and to confirm eligibility or record reasons for screening failure, as applicable.
- The maximum amount of blood collected from each participant over the duration of the study is not expected to exceed 600 mL; however, repeat or unscheduled samples may be taken for safety reasons or for technical issues with the samples.

For details on home healthcare and telemedicine approaches, please refer to [Appendix 10](#).

8.1. Baseline Assessments

Baseline assessments will be captured to ensure characterisation of participants at baseline. The information to be captured is described fully in the SRM; however, in summary it includes but is not limited to:

- Extent of disease (proctosigmoiditis, left-sided or extensive/pancolitis).
- Duration of disease (date of diagnosis).
- Activity of disease.
- Previous treatment(s) for UC and reasons for discontinuation (if discontinued) – for each treatment.
- Smoking status.
- Extra-intestinal manifestations.
- Past medical history.
- Medication history.

8.2. Efficacy Assessments

8.2.1. Clinical Disease Assessments

8.2.1.1. Mayo Score

Clinical disease assessments will be undertaken using the Mayo Score. Multiple derivations will be calculated (described below) to enable characterisation of disease status, whilst also enabling comparison of disease remission and response with previous clinical studies in UC.

- The Complete 4-domain Mayo Score is a 12-point scoring system where disease is evaluated based on stool frequency, rectal bleeding, physician global assessment (PGA) and endoscopic appearance (with **CCI** [REDACTED] associated with an endoscopic score of **po** [REDACTED]).
- The Adapted Mayo Score is a 9-point scoring system where disease is evaluated based on stool frequency, rectal bleeding and endoscopic appearance (with any **CCI** [REDACTED] associated with an endoscopic score of **CCI** [REDACTED] or **CCI** [REDACTED]).
- The Partial Mayo Score is a 9-point scoring system where disease is evaluated based on stool frequency, rectal bleeding and PGA, but no endoscopy component, and will be used to follow changes in these parameters over the course of the study.

The patient reported outcomes of Stool Frequency and Rectal Bleeding for Mayo scores will be calculated from participant eDiary data. To provide a participant's Mayo score status during study conduct, eDiary data will be transcribed into the eCRF for calculation of the Stool Frequency and Rectal Bleeding subscores. Identification of data to be used for calculation of the Mayo score will be based on:

- 3 consecutive days.
 - Where 3 consecutive days are not available, non-consecutive days may be used.
 - For determining eligibility in Screening, 3 days are mandatory. Exceptionally, for determining Responder status at Week 10 double blind and Week 22 Open Label, 2 days may be sufficient, the RAP details how these participants will be handled in the study analysis.
- Within 7 days prior to the endoscopy.
- As close to the date of endoscopy as possible.
- Excluding any days in which bowel preparations are administered.

For further guidance on which days to select in case of missed eDiary entries in any of the targeted days, see SRM for full details. Note that calculations must be made within eCRF to determine Eligibility (prior to Randomisation) and Responder status.

Complete and Adapted Mayo Scores will be calculated from eDiary data, site reported PGA scores and centrally read endoscopy scores at all time points indicated in the SoA (Section 1.3). Definitions of each of the Mayo Score systems, and associated response and remission definitions for each score, can be found in [Appendix 7](#), Section 10.7.

To enable Mayo scoring of stool frequency it is necessary to determine baseline ‘normal’ number of stools per day through discussion between the patient and the Investigator. ‘Normal’ will be defined to the participant as “the number of stools in a 24 hour period when you are not experiencing a UC flare, or when you were in remission”. If the patient reports that they have not attained remission, then the patient will be asked to identify the number of stools he or she had per day before the initial onset of signs and symptoms of UC. This will be used to inform subsequent Mayo scoring of stool frequency.

8.2.1.2. Ulcerative Colitis Endoscopic Index of Severity

The Ulcerative Colitis Endoscopic Index of Severity (UCEIS) will be used as an additional tool to assess disease activity based on endoscopic vascular pattern, bleeding, erosions and ulcerations (see SRM for detail). It has been shown to accurately reflect overall assessment of endoscopic severity of UC and predict outcomes in severe disease [Xie, 2018]. Its broader range than the Mayo endoscopic score facilitates assessment of the dose-response relationship [Travis, 2012]. The UCEIS will be collected and scored centrally at all time points indicated in the SoA (see Section 1.3).

8.2.2. Histological Disease Assessments

Definitions of histological remission for histological disease assessments are included in the RAP. During the study, the Robarts Histopathology Index, Nancy Histological Index and Geboes Score will be assessed by central reading of gut pinch biopsies. Key domains for scoring of the indices include: chronic inflammatory infiltrate; neutrophils in the epithelium; lamina propria neutrophils (and eosinophils – Geboes Score); erosion and ulceration; and crypt destruction (Geboes Score).

8.2.3. Extraintestinal Manifestations

Extraintestinal manifestation (EIM) assessments are key clinical manifestations related to UC, and will be evaluated at screening and during the study (see SoA, Section 1.3). A number of EIMs will be assessed including but not limited to:

- Peripheral arthritis.
- Axial arthropathy.
- Dermatological manifestations.
- Uveitis.
- Primary sclerosing cholangitis.
- Oral aphthous ulceration.

If present, EIMs will be scored by the Investigator as detailed in the SRM.

8.2.4. Patient Reported Outcomes

All patient reported outcome (PRO) questionnaires will be completed on an electronic device. A Bowel Symptom Diary will be completed by participants daily at home, throughout the study. PRO measures for health outcomes assessment will be completed at

study visits, before any other study assessments, also on an electronic device. Sites will receive notification from the ePRO vendor when patients fail to complete the ePRO diary or other measures, and should follow-up with the patient to ensure completeness for all PRO questionnaires.

